Studies have reported a series of measurements to demonstrate the efficacy of E-stim therapy such as thigh circumference, strength of lower extremity muscles (isometric or isotonic dynamometry, MRC score), and quality of life questionnaires. In our previously mentioned trial (NCT04685213, H-47781-A), dynamometer tests were difficult to obtain due to patient sedation, medical paralyzation or intubation. Moreover, calf circumference was altered in patients with present edema. Even though we did not assess MRC score or quality of life questionnaires, lack of feasibility also applies for this measurements because it requires awareness of the patient. Therefore, objective measurements that do not depend or interfere with the patient status are needed to evaluate the progress/effectiveness of E-Stim therapy.

Quantitative neuromuscular ultrasound is emerging as a potential research and diagnostic tool but is not a clinical standard of care. Although creatinine kinase may be elevated in patients with ICUAW, there are no validated biomarkers used for diagnosing ICUAW. In our previous trials (NCT04685213, H-47781-A; NCT05198466, H-47781-B), surface electromyography (sEMG) has been able to detect muscle endurance in response to E-Stim. This parameter was associated with a decreased likelihood to fall at the time of ICU discharge, and an increase in muscle perfusion of Post-COVID-19 patients with neuromuscular sequelae. This suggests that sEMG can be an objective and feasible muscle assessment for ICU patients regardless of awareness. Moreover, Moss et al. reported that sural sensory nerve conductive assessment yielded a sensitivity of 100% with a specificity of 81% to diagnose neuromyopathy due to ICUAW. Therefore, we purpose to utilize a nerve conductive/amplitude assessment tool of the sural nerve called DPN Check device (Neurometrix Inc.).

Lastly, our institution has a high volume of intensive care units (N=10) (Baylor St Luke's Medical Center, Houston, TX, USA) supervised by specialists in critical, intensive, and post-surgical care. Therefore, we believe our institution is a suitable place to perform this study.

Section D: Purpose and Objectives

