- Less than 48 hours of ICU stay - Major foot problems such as active lower extremity wounds, major foot deformity (e.g., Charcot Foot), and/or previous major amputations - Demand-type cardiac pacemaker, implanted defibrillator, or other implanted electronic devices - Any conditions that may interfere with outcomes or increase the risk of the use of neuromodulation therapy based on the judgement of clinicians

F2. Procedure

Patients admitted to the ICU within 2 days will be eligible and enrolled in the study after obtaining consent form as previously indicated.

Then, we will perform baseline measurements that include:

(Primary outcomes) Myopathy test: gastrocnemius muscle endurance (surface electromyogram, Trigno Delsys) in response to 5 minutes of neuromodulation; and muscle thickness (gastrocnemius muscle ultrasound, Vscan Air).

(Secondary outcomes) Perfusion test: Plantar foot perfusion parameters (near infrared spectroscopy, Kent Imaging System). The Snapshot NIR camera is a non-invasive imaging device that visualizes and maps tissue oxygen saturation, oxyhemoglobin, and deoxyhemoglobin from the microvascular network of a particular area of the skin. The SnapShot NIR camera is classified as an oximeter, tissue saturation device. As indicated in the 510 (k) summary by Kent Imaging, the NIR SnapshotNIR is a class II device intended for use by healthcare professionals as a non-invasive tissue oxygenation measurement system that reports an approximate value of: - oxygen saturation (StO2), - relative oxyhemoglobin level (HbO2), and - relative deoxyhemoglobin (Hb) level. SnapshotNIR is based on multispectral imaging technology and performs spectral analysis at each point in a two-dimensional scanned area producing an image displaying information derived from the analysis. In the present study, this device has no diagnostic, decision making, nor treatment intent, it is an assessment camera for tissue perfusion status in real time. The camera is positioned 30-50 cm away from the desired skin area, and a picture is taken. The pictures will be collected from the plantar foot of the patients as in our previous protocols for electrical stimulation (H-47781, H-50753). The data collected will determine whether lower-extremity electrical stimulation improves perfusion to the distal foot by comparing each time point vs baseline and by group comparison (placebo vs active device).

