Statistical Design: Independent t-test, U-test, or Chi-square (depends on type of variables) will be used to compare between groups (IG, and CG for key baseline descriptors including demographics and relevant clinical characteristics). Those descriptors which showed statistical significant difference will be considered as covariates for adjusting the results in the following assessments. Appropriate mixed models (linear for continuous or Generalized Estimating Equations (GEEs) for non-continuous or non-parametric variables) will be used to test the intervention effect for each of the primary or secondary outcomes. Results will be adjusted by covariates as described above.

P-values of 0.05 or less will be considered statistically significant based on a two-sided test unless otherwise noted. All variables will be tabulated descriptively at each scheduled time point (baseline, follow up and discharge date). For each continuous variable, the analyses will include the mean, standard deviation, minimum and maximum. For each categorical variable, the summary will include frequencies and percentages. Each variable will be analyzed using all available data. Baseline variables will be summarized using descriptive statistics. We assume that a successful intervention is also helpful to maintain subjects muscle mass, reduce neuromyopathy signs and increase perfusion. The measured parameters (e.g. sEMG, US, strength, Kent imaging, DPN Check, etc.) should change substantially from baseline to the end of the intervention. For example, the EMG amplitude values should show increased voltages. Next, for all continuous variables, pre-treatment scores will be regressed on post-treatment scores to form residualized change scores (e.g. sEMG, US, strength, Kent imaging, DPN Check, etc.). Correlations will then be generated among these scores to determine whether changes in sEMG factors are related appropriately with increases in (clinically assessed) functional capacities and self-report measures of activities at 1 month post-hospital discharge. ANOVA test will be used to examine significant difference between patients with severe risk factors for prolonged ICU stage (e.g. age, BMI, cardiovascular morbidities). Moderator effects will also be examined for exploratory purposes.

Section H: Potential Risks/Discomforts

H1. Potential Risks/Discomforts

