Subjects will be recruited from the hospital. They may get some referrals from other collaborators. In order to recruit or identify subjects, we will screen our patient charts for eligible subjects. The COI will identify eligible subjects and alert the coordinator. The coordinator will review all the details of the study with the subject and/or their family. If the subject agrees to participate in the study, they will be screened and then enrolled into the study. The recruitment process will be the same for English and Spanish patients, we are only adding the Spanish consent in the event a subject who's primary language is not English can be consented. We have a bilingual Research Coordinator who will explain the consent and conduct the visit in the subjects primary language.

We will be conducting the study during the first 48 hours of intubation at the ICU. Consent will be obtained from the patient legal authorized representative (LAR). The LAR is determined as an individual or judicial or other body authorized under applicable law to make decisions on behalf of another individual. The LAR may provide consent on behalf of a prospective subject to the subject's participation in research. The terms surrogate decision maker or surrogate consent are also sometimes used. The LAR may be a family member or caregiver who has the legal authority to grant consent on behalf of another who has been invited to participate in research. The LAR will give consent by agreeing with the procedures/benefits/ risks and participation. All questions/doubts from the LAR about the study will be clarified. When the patient regain consciousness or ability to consent, he/she will be fully informed about the study, and will the research staff will obtain their signature. In order to reconsent, the patient will need to be fully awake in time, space, and person. The signed consent form will be maintained in research records.

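### Neuromuscular blockade at the baseline sEMG is neither recorded nor modelled, which costs precision on a primary outcome and distorts its change scores

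*Combined protocol and SAP*

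**What the plan says.** - **Background (before Section D).** In the sponsor's earlier ICU COVID-19 trial, "dynamometer tests were difficult to obtain due to patient sedation, medical paralyzation or intubation". The text then argues from the sponsor's previous trials that "sEMG can be an objective and feasible muscle assessment for ICU patients regardless of awareness".
- **Timing.** F2 states "Patients admitted to the ICU within 2 days will be eligible and enrolled in the study", with baseline tests following consent. J2 states "We will be conducting the study during the first 48 hours of intubation at the ICU". Follow-up is at day 3, then weekly to 4 weeks or discharge (F2).
- **Population.** F1 admits patients whether intubated or not. E2 and F1 add post-surgical ICU patients.
- **Outcome.** F2 makes gastrocnemius endurance by sEMG, recorded in response to five minutes of stimulation, a primary outcome together with muscle thickness. Section I also lists sEMG as primary, alongside the nerve conduction test.
- **Analysis (G2).** "Each variable will be analyzed using all available data". As an illustration of the change expected from baseline, "the EMG amplitude values should show increased voltages". The intervention effect is tested by mixed models or GEE. Covariates are those baseline descriptors that differ significantly between groups. Residualised change scores are formed and correlated with function and self-report.

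No section asks for blockade or sedation to be recorded when an sEMG reading is taken, says how a reading under blockade is handled, or names blockade as a covariate.

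**The concern.** The argument for sEMG is that the patient need not be awake. That covers sedation. Neuromuscular blockade is different, because it can reduce the electrical response of the muscle, which is the quantity being measured. The protocol itself reports medical paralysis in ICU patients at this hospital group's earlier trial, and it sets the baseline early in the stay, when blockade is plausible for some intubated or post-surgical patients. If blockade has ended by a later visit, that patient's sEMG can rise with no change in the muscle, in the direction G2 expects from a successful intervention.

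Three uses of the data are exposed. Change from baseline within an arm can mislead. The between-group model loses precision because the baseline is a noisier predictor. The residualised change scores that G2 correlates with later function would partly sort patients by their drug state at baseline.

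**Working it through.** The plan has no figure to reproduce: G1 gives a convenience sample of 40, with no effect size, SD or power. The documents supply 20 per arm (F1) and two-sided 0.05 (G2). Everything else here is assumed:

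- fraction p paralysed at baseline, 10% to 30%, and none later
- drop D = 2 SD in a paralysed patient's reading
- true baseline/follow-up correlation 0.6, with unit SD at both times
- paralysis unrelated to the true muscle level.

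**Formulas**
- Apparent mean rise with no true change = pD
- Added baseline variance a = D²p(1−p)
- Variance of change = 2 − 2(0.6) + a
- Observed correlation r = 0.6/√(1+a)
- Baseline-adjusted error variance = 1 − 0.36/(1+a)

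| p | pD | a | Var(change) | r | Adjusted error variance |
|---|---|---|---|---|---|
| 0 | 0 | 0 | 0.80 | 0.60 | 0.640 |
| 0.10 | 0.2 | 0.36 | 1.16 (+45%) | 0.51 | 0.735 (+15%) |
| 0.20 | 0.4 | 0.64 | 1.44 (+80%) | 0.47 | 0.780 (+22%) |
| 0.30 | 0.6 | 0.84 | 1.64 (+105%) | 0.44 | 0.804 (+26%) |

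**Smaller drop.** With D = 1, a = 0.09 and 0.21 at p = 0.10 and 0.30. Adjusted error variance is 0.670 and 0.702, a rise of 5% and 10%.

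**Which column applies.** G2 does not say whether baseline sEMG enters the mixed model as a covariate. If it does, the last column applies. If change scores are compared, the Var(change) column applies.

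**Power (normal approximation).** Take an effect with 80% power under a clean baseline (1.96 + 0.84 = 2.80 standard errors). At p = 0.10, 2.80 × √(0.640/0.735) − 1.96 = 0.65, which is 74% power. At p = 0.30, 2.80 × √(0.640/0.804) − 1.96 = 0.54, which is about 70%.

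**Type I error.** In 10,000 simulated trials per setting with no treatment effect (10% to 50% paralysed, shift of 1 or 2 SD in the change score), the between-arm t-test rejected in 4.6% to 5.2% of trials. It stays at its nominal level.

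**Chance imbalance.** With two arms of 20, the probability that the counts of paralysed patients differ by 4 or more is 6%, 16% and 23% at p = 0.10, 0.20 and 0.30. A difference of 4 is 4/20 = 0.2 in proportion. It moves a change-score comparison by 0.2 × 2 = 0.4 SD. A baseline-adjusted comparison moves by 0.4 × 0.6/(1+a) = 0.18, 0.15 and 0.13 SD.

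**Residualised change.** Reading G2 in the usual sense (follow-up adjusted for baseline), the slope is 0.6/(1+a). Patients paralysed at baseline then score higher than the others by 2 × 0.6/(1+a), which is 0.88 SD at p = 0.10 and 0.65 SD at p = 0.30, with no true difference.

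**With a blockade indicator.** If the drop is constant, adding baseline blockade status beside baseline sEMG recovers the true baseline exactly, and the error variance returns to 0.64.

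**The case against.** The strongest reply is that this is a 1:1 randomised trial with a placebo device. Lifting of blockade affects both arms alike in expectation, and the simulated type I error confirms it. This stands. A reader might infer that the plan would credit the device with what is really a drug wearing off, but the documents do not support that. G2 tests the intervention effect between groups and specifies no within-arm test for sEMG. The comparison of each time point with baseline in F2 concerns foot perfusion and sits beside a group comparison. The voltage sentence in G2 is offered as an example, not as a success criterion.

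A reader might also infer that in paralysed patients sEMG measures drug state rather than muscle. That goes too far. The reading is taken during electrical stimulation, the Background describes that stimulation as reaching deep fibres, and nothing says how far blockade suppresses the response.

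The inputs are also open to challenge. The paralysis report comes from a COVID-19 ICU trial, while this trial takes non-intubated and post-surgical patients too. F1 excludes ICU stays under 48 hours, which may place baseline later. Blockade that persists to day 3 or starts after baseline would shrink or reverse the shift. These points limit the size that can be claimed; they do not supply the missing record.

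F1 lets clinicians exclude patients with conditions that may interfere with outcomes. That helps in part, but it is discretionary, acts only at entry, does not name paralysis and sets no rule for readings.

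Finally, this is a pilot, and sEMG is not its only primary measure. However, F1 gives feasibility of the objective measurement tools as a purpose, so whether sEMG can be interpreted under ICU conditions is one of the questions the pilot should answer.

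**Conclusion.** The point holds in limited form. Some patients may be under blockade at the baseline sEMG, and the plan neither records this nor accounts for it. The randomised comparison is not systematically biased. It would be less precise and open to chance imbalance, and change from baseline and the residualised-change correlations would be distorted.

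The size cannot be known from the documents. Under the 2 SD assumptions the loss is about 15% to 26% in baseline-adjusted error variance, and about 5% to 10% if the drop is 1 SD. If no patient is paralysed at baseline, or blockade leaves the stimulated response unchanged, there is no loss. This is a worthwhile, inexpensive correction and not a threat to the validity of the between-group test.

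**What to change.** **F2.** At each sEMG test, record from the chart whether neuromuscular blockade is active (yes/no) and the current sedation score.

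**G2.**
- Prespecify baseline sEMG and baseline blockade status as covariates in the between-group sEMG model, whether or not they differ significantly between arms. Use both in forming the residualised change scores.
- State that the efficacy conclusion rests on the between-group contrast and not on within-arm rises.
- Add a sensitivity analysis that excludes readings taken under blockade.

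Declaring such readings not evaluable in the primary analysis would be a weaker choice. Under the assumptions above, precision weighting gives an error variance of 1/(0.9/0.64 + 0.1) = 0.66 to 1/(0.7/0.64 + 0.3) = 0.72, against 0.64 with the covariate. It would also drop post-randomisation readings from the main result, and deferring a baseline would need a baseline window that the protocol does not define.

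**Cost.** One or two chart fields per visit, one extra model term (one degree of freedom), and a sensitivity analysis on fewer readings that itself omits some post-randomisation data. The covariate deals with blockade at baseline only; later blockade is addressed only by the sensitivity analysis. Care and sample size do not change.

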Aim 1. Acceptability: To examine feasibility and acceptability of lower extremity neuromodulation in patients at risk of ICUAW. H1.1: The adherence to daily use of lower extremity neuromodulation is more than 80% among the IG. Adherence is defined as the use of lower extremity neuromodulation at least one hour per day for at least 4 days per week. H1.2: The perceived acceptability, and perceived benefit would be high among IG.

Aim 2. Proof of concept effectiveness: To examine effectiveness of lower extremity neuromodulation for intubated patients at risk of ICUAW H1.1: E-Stim will improve motor function including muscle endurance and thickness, nerve conductivity and amplitude, by utilizing objective assessments (surface electromyography, ultrasound, dynamometry), after 4 weeks of application or hospital discharge, whichever comes first. H1.2: E-Stim will improve lower extremity nerve function and tissue perfusion after 4 weeks of application or until hospital discharge, whichever comes first. The nerve function parameters will be measured with assessed with a digital test (DPN Check) for peripheral neuropathy and the perfusion parameters will be assessed using a near infrared spectroscopy using a validated imaging system (Kent Imaging System).

Section E: Protocol Risks/Subjects

E1. Risk Category

Category 1: Research not involving greater than minimum risk.

E2. Subjects

Gender:

Both

Age:

Adult (18-64 yrs), Geriatric (65+ yrs)

Ethnicity:

All Ethnicities

Primary Language:

English, Spanish

Groups to be recruited will include:

Patients

Which if any of the following vulnerable populations will be recruited as subjects?

Cognitively impaired

Vulnerable populations require special protections. How will you obtain informed consent, protect subject confidentiality, and prevent undue coercion?

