E4. Neonates

Will neonates of uncertain viability or nonviable neonates (as described in 45 CFR 46 Subpart B) be enrolled in the research?

No

E5. Children

Will children be enrolled in the research?

No

Section F: Design/Procedure

F1. Design

Select one category that most adequately describes your research:

c) Pilot

Discuss the research design including but not limited to such issues as: probability of group assignment, potential for subject to be randomized to placebo group, use of control subjects, etc.

We will prospectively recruit 40 patients at risk of ICUAW. Sample size is convenient and designed to explore acceptability and feasibility of objective tools for measurement. Eligible participants will be screened at BSLMC. Those who satisfied the inclusion and exclusion criteria and signed the informed consent form will be randomly assigned with ratio of 1:1 into two groups. Consenting will be performed with a legal authorized representative (LAR) that is present. When the subject regains consciousness and is aware in time, space, and person, he/she will be re-consented. If the subject decline to continue participation in the study, the subject will be withdrawn. The informed consent will be obtained from all participants and their LAR.

Sub-population: Post-surgical patients that are admitted to the ICU will be consented either before surgery, or by a LAR on the day of surgery as described above.

The study will be double-blinded (clinicians and patients) in intervention (IG) and control (CG) group. Both cohorts will be followed-up and monitored at 3 days, and then weekly for a total period of 4 weeks or until hospital discharge, whichever comes first. • Intervention group (IG). The IG (n=20) will be undergoing E-Stim therapy with an active device during the hospitalization period until 4 weeks or discharge, whichever comes first. To deliver E-Stim, 2 electrodes will be placed in each proximal gastrocnemius and Achilles tendons. • Control Group (CG). The CG (n=20) will be undergoing E-Stim therapy with a placebo device (5-10% currents) as described in the IG.

Inclusion Criteria:

-Any patient older than 18 years old admitted to the ICU within two days. -Patient can be intubated with ventilatory assistance or not.

Exclusion Criteria:

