Neuropathy test: Sural nerve conduction/amplitude assessment (neuropathy, DPNCheck Device by Neurometrix Inc)

Biomarkers tests: Creatinine kinase, C-reactive protein, creatinine, potassium, myosin, serum lactate, arterial SpO2, duplex ultrasound for DVT will be collected from the electronic medical records. If biomarkers were not collected as a standard/regular procedure in the ICU; data will not be extracted from the electronic medical records. Research staff will not draw any blood samples.

Then, the patients will receive an individually programmed device to deliver neuromodulation to both gastrocnemius muscles simultaneously. The frequency of therapy will be 1 hour daily, and the duration will be up to 4 weeks or until hospital discharge, whichever comes first.

The coordinator will provide the ICU staff with a weekly spreadsheet showing utilization (therapy sessions/day) so compliance can be monitored. Also, the devices will monitor the time of usage to confirm hours of effective neuromodulation therapy to the skin.

Follow-up assessments will be performed at 3 days, and then weekly until 4 weeks or until hospital discharge, whichever comes first, by the research staff. The follow-up assessment will be identical to the baseline assessment.

In the final visit, we will assess muscle strength (ankle dynamometer, RoMech Digital Hanging Scale).

Additional measurements: - 1-month post-hospital discharge phone questionnaires: instrumental activity of daily living scale (IADL), community engagement (the Life Space Questionnaire), independence in daily living activities (KATZ), and anxiety (BAI).

Section G: Sample Size/Data Analysis

G1. Sample Size

How many subjects (or specimens, or charts) will be used in this study?

Local: 40 Worldwide: 40

Please indicate why you chose the sample size proposed:

Sample size is convenient and selected based on available resources to demonstrate feasibility and the proof of concept effectiveness of neuromodulation therapy for patients admitted to ICU and post-ICU. We plan to recruit 40 eligible subjects.

G2. Data Analysis

Provide a description of your plan for data analysis. State the types of comparisons you plan (e.g. comparison of means, comparison of proportions, regressions, analysis of variance). Which is the PRIMARY comparison/analysis? How will the analyses proposed relate to the primary purposes of your study?

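### Aim 1 hypothesises adherence above 80% in 20 patients, but the plan provides at most a bare percentage, which cannot support that claim at this sample size

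*Combined protocol and SAP*

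**What the plan says.** Section D, Aim 1, H1.1 states the hypothesis: "The adherence to daily use of lower extremity neuromodulation is more than 80% among the IG". It then gives the rule: "Adherence is defined as the use of lower extremity neuromodulation at least one hour per day for at least 4 days per week". It does not say whether the 80% counts patients, patient-weeks or sessions, or how a patient's weeks are combined.

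F1 fixes the group size: "The IG (n=20) will be undergoing E-Stim therapy with an active device". G1 gives the basis for the total of 40: "Sample size is convenient and selected based on available resources to demonstrate feasibility and the proof of concept effectiveness of neuromodulation therapy".

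G2 does not mention adherence. Its mixed models and GEEs "will be used to test the intervention effect for each of the primary or secondary outcomes", and neither F2 nor Section I lists adherence among those outcomes. The remaining G2 analyses are baseline group comparisons, correlations of change scores, ANOVA by risk factor and exploratory moderator analyses. The provision that would cover a yes/no adherence variable is general: "For each categorical variable, the summary will include frequencies and percentages".

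**The concern.** H1.1 is a claim about one arm against a fixed number. The tests in G2 compare arms, correlate changes or compare risk-factor subgroups, and none of them can show that a single arm exceeds 80%. What remains is an observed percentage with no stated measure of its uncertainty.

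With 20 patients that uncertainty is large. If the observed percentage is set directly against 80%, the report can say that H1.1 is supported when true adherence is 80% or lower. H1.1 is the first hypothesis of the first aim and the only one in Aim 1 with a numeric mark. G1 justifies the sample partly by feasibility, so a reader planning a later trial would rely on this result.

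**Working it through.** The documents give no precision or decision-rule figure for adherence, so there is none to reproduce. The check asks what an observed percentage above 80% is worth with 20 patients.

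**Inputs**
- Mark: more than 80% (Section D, Aim 1, H1.1).
- n = 20 in the IG (F1).
- Assumption: each IG patient is classed once as adherent or not, and all 20 are evaluable. The documents do not state this.

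**Step 1. Smallest count above 80%.** 16/20 = 80%, which is not more than 80%. 17/20 = 85% is the smallest count that is.

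**Step 2. How often 17 or more is reached.** With X binomial(20, p), P(X ≥ 17) is the sum over x = 17 to 20 of C(20, x) p^x (1 − p)^(20 − x).

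At p = 0.80:
- x = 17: 1140 × 0.8^17 × 0.2^3 = 0.205
- x = 18: 190 × 0.8^18 × 0.2^2 = 0.137
- x = 19: 20 × 0.8^19 × 0.2 = 0.058
- x = 20: 0.8^20 = 0.012
- Sum: 0.411

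| True adherence | P(17 or more of 20) |
|---|---|
| 70% | 0.107 |
| 75% | 0.225 |
| 80% | 0.411 |
| 85% | 0.648 |
| 90% | 0.867 |

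H1.1 is false in the first three rows.

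**Step 3. Exact (Clopper-Pearson) 95% interval for x of n.** The lower limit is the 0.025 quantile of Beta(x, n − x + 1). The upper limit is the 0.975 quantile of Beta(x + 1, n − x).

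| Count | Observed | Exact 95% interval |
|---|---|---|
| 17/20 | 85% | 62.1% to 96.8% |
| 18/20 | 90% | 68.3% to 98.8% |
| 19/20 | 95% | 75.1% to 99.9% |
| 20/20 | 100% | 83.2% to 100% |

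Only 20/20 has a lower limit above 80%.

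**Step 4. Sensitivity to the interval method.** For 17/20 the two-sided lower limit is 62.1% (exact), 63.1% (Agresti-Coull), 64.0% (Wilson), 65.1% (Jeffreys) or 69.4% (Wald). All are well below 80%.

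**The case against.** The strongest reply is that this is a pilot with a convenience sample and that 80% is a hypothesis. A reader might infer that 80% is a formal success mark or a go/no-go rule. The documents do not support that: no section attaches a decision to it. This part of the reply stands. The point is only that a stated hypothesis needs a stated basis for being called supported.

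A reader might also infer that the plan contains two competing pass marks: 17/20 on the observed percentage, and 20/20 under G2's general rule, "P-values of 0.05 or less will be considered statistically significant based on a two-sided test unless otherwise noted". The documents do not support this either. That rule governs tests that are planned, and G2 plans no one-sample test of adherence against 80%.

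The unit is a fair objection. The devices log usage time (F2), so adherence could be a continuous percentage per patient. G2 would then give a mean, standard deviation, minimum and maximum, from which a standard error follows. If 80% counts weeks or sessions, observations cluster within patients and the binomial figures do not apply. G2's wording also does not rule out adding an interval. These points limit the numbers to the patient-level reading, but on no reading does the plan commit to an interval or say how the estimate is judged against 80%.

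Finally, 17 or more of 20 will still occur 41% of the time at a true 80% after the fix. That is so. The fix changes what may be concluded from that count, not how often it occurs.

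**Conclusion.** The concern holds in a limited form. If each of 20 IG patients is classed once as adherent or not, an observed percentage above 80% arises 41% of the time when true adherence is exactly 80% and 23% of the time at 75%. It therefore cannot by itself support the claim that adherence exceeds 80%, and the plan provides nothing further.

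The lower limit of 62% should not be read as a likely value of true adherence. It is the edge of one interval: at a true 62%, 17 or more of 20 occurs only about 2.5% of the time. The 41% figure is the fairer measure of the problem.

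The finding rests on the patient-level unit and on all 20 patients being evaluable. It concerns the feasibility conclusion under Aim 1 and leaves the analyses of the primary and secondary outcomes untouched. It does not call for a larger sample.

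**What to change.** - **G2:** name adherence, state its unit and denominator, and report the IG estimate with a 95% confidence interval. Use an exact binomial interval if there is one yes/no per patient. If 80% counts weeks or sessions, use an interval that allows for clustering within patient.
- **Section D, Aim 1, H1.1:** describe 80% as a descriptive feasibility benchmark for the observed estimate. State that adherence is concluded to be more than 80% only if the lower confidence limit exceeds 80%. Otherwise report the benchmark as met or not met, with the interval.

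The cost is a few sentences, with no new data and no more patients. The real downside is a weaker headline: 17/20 would be reported as benchmark met, 85%, 95% interval 62% to 97%. On the patient-level reading the stronger conclusion would need 20/20, which occurs 12% of the time at a true 90% (0.90^20 = 0.122) and 36% at a true 95% (0.95^20 = 0.358). The authors should therefore expect to report against the benchmark, not to prove the claim.
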